Patients are routinely followed for two years after undergoing implant-based reconstruction. In this study, we will initially see patients periodically for research visits until tissue expansion has been completed. After implant exchange, we will see patients every 2 weeks for the first month, and every month for the subsequent 4 months. We will then see them every 6 months for the remainder of the two years. Those patients who are removed from treatment will be followed as per our standard of care, which is monthly for the first six months and then every six months for two years. Serious adverse events will be collected for 30 days after the end of treatment, or until death, whichever occurs first. Patients removed from the study for unacceptable treatment-related adverse event(s) will be followed until resolution or stabilization of all treatment-related adverse events to Grade 1 or baseline.

Study drugs:

Zafirlukast 20mg PO BID

Safety assessments:

Safety will be assessed by reviewing adverse events (AEs), laboratory evaluations, physical examination, and spontaneous report. Each patient will be assessed periodically for the development of any toxicity. All AEs and serious AEs (SAEs) will be documented and reported. We will also pay particular attention to adverse events of clinical interest specific to zafirlukast.

Unique aspects of this study:

This is the first study to prospectively investigate the potential of zafirlukast to slow or prevent capsular contracture from occurring.

List of Abbreviations

AE	adverse event
ALP	alkaline phosphatase
ALT	alanine aminotransferase
ANC	absolute neutrophil count
AST	aspartate aminotransferase
BUN	blood urea nitrogen
CBC	complete blood cell (count)
CHR	Committee on Human Research (UCSF IRB)
CR	complete response
CRC	Clinical Research Coordinator
CRF	case report form
CSF	cerebral spinal fluid
CT	computerized tomography
CTCEA	Common Terminology Criteria for Adverse Events
CTEP	Cancer Therapy Evaluation Program
CTMS	Clinical Trial Management System
DFS	disease-free survival
DLT	dose limiting toxicity
DSMC	Data and Safety Monitoring Committee
DSMP	Data and Safety Monitoring Plan
FDA	Food and Drug Administration
GCP	Good Clinical Practice
HDFCCC	Helen Diller Family Comprehensive Cancer Center
HGB	Hemoglobin
HIV	human immunodeficiency virus
ICH	International Conference on Harmonization
IND	investigational new drug application
IP	investigational product
IRB	Institutional Review Board

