4.4 Packaging and Labeling of Study Drugs

Drugs will be packaged and labeled per UCSF institutional standards, adhering to applicable local and federal laws.

5 TREATMENT PLAN**5.1 Dose Modifications and Dosing Delays**

Zafirlukast will be administered in 20mg tablets as a single dose. Although zafirlukast is available as a 10mg tablet as well, there will be no dose modification. Should a patient be unable to tolerate the standard dose of 20mg, she will be removed from this study. Zafirlukast should be stopped prior to expander implant exchange

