6.2 Assessments and procedures during treatment

Once the patient is confirmed to be eligible based on screening assessments, the following study assessments will be performed. See Table 6 for summary. Cohort A participants will begin treatment with zafirlukast on post-operative day one (+/- 5 days) following placement of tissue expander(s) after the participant is determined safe from a surgical recovery standpoint. Cohort A participants will take zafirlukast twice per day until the patient has completed expansion of the tissue expander. Zafirlukast should be stopped prior to expander implant exchange. Patients will be randomized on the day of surgery by a study personnel other than the surgeon. The surgeon and patient will be informed of the assigned cohort immediately post-surgery.

Research Visits (+/- 1 week)

- Physical examination (including height and weight)
- Vital signs (blood pressure, pulse rate, respiratory rate, temperature)
- Con-Med and AE review
- CBC with differential and platelet count
- Serum biochemical panel including creatinine, fasting glucose, potassium, sodium, chloride, bicarbonate
- Liver function tests: alkaline phosphatase, ALT/AST, total bilirubin (only for Cohort A)

Expander-Implant Exchange

- Tissue specimen collection

End of Treatment (14 days (+/- 3 days) of expander-implant exchange)

- Medical history, physical examination (including height and weight), vital signs (blood pressure, pulse rate, respiratory rate, temperature)
- CBC with differential and platelet count
- Serum biochemical panel including creatinine, fasting glucose, potassium, sodium, chloride, bicarbonate
- Liver function tests: alkaline phosphatase, ALT/AST, total bilirubin (only for Cohort A)
- Con-Med and AE review

Follow up

Patients are followed for two years after implant reconstruction. After implant exchange we will see patients every 2 weeks for the first month, every month for the subsequent 4 months, and, every 6 months for the remainder of the two years. For those patients removed from the treatment, they will be followed as per our standard of care which is monthly for the first six months and then every six months for a total of two years.

- Physical examination (including height and weight), vital signs (blood pressure, pulse rate, respiratory rate, temperature)

Table 6. Schedule of Study Procedures and Assessments

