Period/ Procedure	Screening ⁹	Treatment period (+/- 1 week)				Expander- implant exchange	End of Treatment	Follow up visits ⁵
Study Day/Visit Day	Days -28 to Day 1	Mastectomy and Tissue- expander placement (week 0)	Day 15-21 (wk 2)	Day 29-35 (wk 5)	Day 71-77 (wk 11)	Day 113-119 (wk 17) ⁸		
Informed Consent	x							
Baseline Conditions ¹	x							
Tissue Specimen Collection						x		
Zafirlukast ⁶		x						
Medical History	x						x	
Vital Signs	x		x	x	x	x	x	x
Physical Exam	x		x	x	x	x	x	x
Con-med and AE review ⁷		x					x	
CBC w/diff ²	x		x	x	x	x	x	
Chemistry ³	x		x	x	x	x	x	
Liver Function Tests ⁴	x			x			x	
Pregnancy Test (HCG)	x							

1. Baseline conditions assessment per DSMC policy.
2. Including CBC with differential and platelet count.
3. Including creatinine, fasting glucose, potassium, sodium, chloride, bicarbonate.
4. Including alkaline phosphatase, ALT/AST, total bilirubin. For Cohort A only on week 5 and EOT. Alkaline phosphatase is not required for screening.
5. Patients are followed for two years after implant reconstruction. After implant exchange we will see patients every 2 weeks for the first month, every month for the subsequent 4 months, and, every 6 months for the remainder of the two years. For those patients are removed from treatment, they will be followed as per our standard of care which is monthly for the first six months and then every six months for a total of two years.
6. 20mg PO twice per day from Day 1 to Treatment Termination for Cohort A only. Treatment may continue until tissue expansion is complete. Zafirlukast should be stopped prior to expander implant exchange.
7. Con-med and AE review begins 28 days prior to treatment and continues 30 days after treatment termination.
8. As needed .
9. Screening procedures must be completed prior to mastectomy and tissue-expander placement.

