6.4 Duration of Therapy

In the absence of treatment delays due to adverse events, treatment may continue until tissue expansion is complete or until:

- Illness that prevents further administration of treatment
- Unacceptable adverse event(s)
- Patients decides to withdraw from the study
- Significant patient non-compliance with protocol
- General or specific changes in the patients' condition render the patient unacceptable for further treatment in the judgment of the investigator.

Patients are routinely followed for two years after undergoing implant based reconstruction. In this study we will initially see patients periodically for research visits until tissue expansion has been completed. After implant exchange we will see patients every 2 weeks for the first month, and every month for the subsequent 4 months. We will then see them every 6 months for the remainder of the two years. Those patients who are removed from treatment will be followed as per our standard of care, which is monthly for the first six months and then every six months for two years. Serious adverse events will be collected for 30 days after the end of treatment, or until death, whichever occurs first. Patients removed from treatment for unacceptable treatment related adverse event(s) will be followed until resolution or stabilization of all treatment related adverse events to Grade 1 or baseline.

Subjects may withdraw consent at any time for any reason, or be dropped from the trial at the discretion of the investigator should any untoward effect occur. In addition, a subject may be withdrawn by the investigator if enrollment into the trial is inappropriate, the trial plan is violated, or for administrative and/or other safety reasons.

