6.9 Prohibited Concomitant Medications

Subjects are prohibited from receiving the following therapies during the Screening and Treatment Phase of this trial:

- Anti-cancer systemic chemotherapy or biological therapy

Subjects who, in the assessment by the investigator, require the use of any of the aforementioned treatments for clinical management should be removed from the trial. Subjects may receive other medications that the investigator deems to be medically necessary.

Potential Drug Interactions:

The following drug interaction studies have been conducted with zafirlukast

- Co-administration of multiple doses of zafirlukast (160 mg/day) to steady-state with a single 25 mg dose of warfarin (a substrate of CYP2C9) resulted in a significant increase in the mean AUC (+63%) and half-life (+36%) of S-warfarin. The mean prothrombin time increased by approximately 35%. The pharmacokinetics of zafirlukast were unaffected by co-administration with warfarin.

- Co-administration of zafirlukast (80 mg/day) at steady-state with a single dose of a liquid theophylline preparation (6 mg/kg) in 13 asthmatic patients, 18 to 44 years of age, resulted in decreased mean plasma concentrations of zafirlukast by approximately 30%, but no effect on plasma theophylline concentrations was observed.
- Co-administration of zafirlukast (20 mg/day) or placebo at steady-state with a single dose of sustained release theophylline preparation (16 mg/kg) in 16 healthy boys and girls (6 through 11 years of age) resulted in no significant differences in the pharmacokinetic parameters of theophylline.
- Co-administration of zafirlukast dosed at 40 mg twice daily in a single-blind, parallel-group, 3-week study in 39 healthy female subjects taking oral contraceptives, resulted in no significant effect on ethinyl estradiol plasma concentrations or contraceptive efficacy.
- Co-administration of zafirlukast (40 mg/day) with aspirin (650 mg four times daily) resulted in mean increased plasma concentrations of zafirlukast by approximately 45%.
- Co-administration of a single dose of zafirlukast (40 mg) with erythromycin (500 mg three times daily for 5 days) to steady-state in 11 asthmatic patients resulted in decreased mean plasma concentrations of zafirlukast by approximately 40% due to a decrease in zafirlukast bioavailability.

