9.1 Analyses Plans

This is an intention to treat analysis. All patients who were randomized will be evaluated.

Data will be summarized using descriptive statistics by study cohorts. For continuous variables, descriptive statistics will include the number of non-missing values, mean, standard deviation, median, minimum and maximum. For categorical variables, descriptive statistics will include counts and percentages per category by study cohorts.

Primary analysis:

The primary objective of the trial is to determine the capsule contracture between the two study cohorts and the primary efficacy outcome in this trial is capsule thickness at the time of expander-implant exchange. Capsule thickness will be determined by averaging thickness from three separate specimens per patient. The capsule thickness will be analyzed by study cohorts, and t-tests and descriptive statistics with mean, standard deviation and 95% confidence intervals will be used for significance. Missing data will not be imputed. An alpha level of 0.05 will be considered significant for the primary endpoint. For exploratory analysis, the primary endpoint of capsule thickness will be presented as mean \pm SEM and evaluated using analysis of variance (ANOVA) with factors including study cohort, radiotherapy and length of drug treatment.

Secondary Analysis:

For secondary objectives of the trial, we will determine the level of fibrosis and presence of collagen from the biopsy specimens. The level of fibrosis and the presence of collagen will be analyzed descriptively as continuous levels and as ordinal levels with mean, standard deviation and 95% confidence intervals. The difference in the level of fibrosis and relative presence of collagen between study cohorts will be compared using t-tests for significance.

Similar statistical methods will also be employed to analyze the capsule tissue that is removed at the time of expander-implant exchange to determine the level and presence of collagen, fibroblasts and myofibroblasts.

Confounding Factors:

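### Section 9.1 declares intention to treat, but Sections 5.1, 6.9 and 6.4 remove patients from the study after randomisation and nothing says their capsule is still collected at exchange

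*Combined protocol and SAP*

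**What the plan says.** **Analysis.** Section 9.1: "This is an intention to treat analysis. All patients who were randomized will be evaluated". The same section makes capsule thickness at exchange the primary outcome, compares cohorts by t-test and rules out imputation. Section 6.2 places randomisation on the day of surgery, so removals during treatment come after it.

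**Leaving the study or trial.**
- Section 5.1: "Should a patient be unable to tolerate the standard dose of 20mg, she will be removed from this study". Only a patient allocated to zafirlukast can meet this rule.
- Section 6.9, on patients who need systemic anti-cancer therapy: they "require the use of any of the aforementioned treatments for clinical management should be removed from the trial". The prohibition covers both screening and the treatment phase.
- Section 6.4, closing paragraph: subjects may "be dropped from the trial at the discretion of the investigator should any untoward effect occur". They may also be withdrawn for other reasons, including violation of the trial plan.

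**Leaving treatment only.**
- Section 6.2, follow-up: "For those patients removed from the treatment, they will be followed as per our standard of care". Table 6, note 5, says the same, and the synopsis and Section 6.4 have equivalent text.
- Section 6.4: "Patients removed from treatment for unacceptable treatment related adverse event(s) will be followed until resolution or stabilization". The synopsis has the same sentence with a different status: "Patients removed from the study for unacceptable treatment-related adverse event(s) will be followed until resolution or stabilization".

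**At and after removal.** Section 6.6.1 asks for the applicable final-visit activities at the time of discontinuation. Section 8.5 follows patients taken off study for unacceptable adverse events for 30 days or until the event resolves or stabilises. Neither mentions capsule collection.

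**Collection.** Sections 3.1 and 6.2 and Table 6 attach specimen collection to the exchange operation and do not mention removed patients. Section 7.0 says a portion of capsule is normally excised in routine care.

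**The concern.** An intention-to-treat analysis needs the outcome from patients who stop the drug, as far as it can be obtained. A site that follows Section 5.1 as written would treat an intolerant patient as out of the study and could reasonably take no research specimen at her exchange. A specimen not taken then cannot be recovered later.

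The primary t-test would then be a complete-case comparison. The loss need not be balanced: one removal rule acts only in the drug arm, and the trial is open-label, so discretionary removals may also depend on arm. If thickness is related to the reason for removal, the retained drug-arm patients no longer compare like with like against the control arm.

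**Working it through.** **1. Reading the sections together.** For a randomised drug-arm patient who cannot tolerate 20 mg:

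| Source | Status | Capsule at exchange? |
|---|---|---|
| 5.1 | out of the study | not stated; literally no |
| 6.2, 6.4, Table 6 note 5 | off treatment, followed for two years | not stated; collection plausible |
| Synopsis, adverse-event sentence | out of the study | not stated |
| 6.4, same sentence | off treatment | not stated |
| 6.6.1 | final-visit activities at discontinuation | not mentioned |
| 8.5 | off study, 30 days or until resolution or stabilisation | not mentioned |
| 3.1, 6.2, Table 6 | collection at exchange, in general terms | not restricted to patients on drug |
| 9.1 | every randomised patient evaluated | implies yes |

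Table 6 schedules visits out to week 17 (the last as needed). A patient removed in the first weeks could complete a 30-day follow-up before her exchange.

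**2. The plan's own power.** Inputs from Section 9.0: means 2.4 and 1.2 mm (difference 1.2), SD 2 mm, two-sided alpha 0.05, t-test, 45 evaluable per cohort. Noncentrality = difference / [SD × √(1/n₁ + 1/n₂)].
- 45 and 45: 1.2 / (2 × 0.2108) = 2.846, power 80.4%. The stated figure of more than 80% reproduces, with almost no margin.
- 41 and 41: 1.2 / (2 × 0.2209) = 2.717, power 76.5%.

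**3. Bias if removed drug-arm patients are not measured.** The documents give no removal rate by arm and nothing linking removal to thickness, so these inputs are assumptions: no true effect, 45 randomised per arm, SD 2 mm, loss in the drug arm only at f = 10% (the plan's overall attrition figure) or 5%. With gap g = mean thickness of removed minus retained patients, the drug-arm mean shifts by −f × g. At 10% loss the analysed sizes average 40.5 and 45, the standard error is 2 × √(1/40.5 + 1/45) = 0.433 mm, and a 1.2 mm gap gives noncentrality 0.12 / 0.433 = 0.277.

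| Loss, drug arm only | Gap (mm) | Shift (mm) | Type I error |
|---|---|---|---|
| 10% | 0 | 0 | 5.0% |
| 10% | 0.4 | 0.04 | 5.1% |
| 10% | 0.6 | 0.06 | 5.2–5.3% |
| 10% | 1.2 | 0.12 | 5.7–5.9% |
| 10% | 1.95 | 0.195 | 7.2–7.3% |
| 5% | 1.2 | 0.06 | 5.2% |
| 5% | 1.95 | 0.10 | 5.5–5.6% |

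Ranges span the noncentral-t calculation and simulations of 200,000 trials per cell, in which removal depended on a latent variable correlated with thickness. A 1.95 mm gap at 10% loss corresponds to a correlation of 0.5. With 10% lost in both arms and the same gap, the shift was within 0.002 mm of zero and type I error 4.9–5.1%.

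**4. Power if patients who stopped early are measured.** Assume 10% of the drug arm stops early.
- No benefit in those patients: difference 1.2 × 0.9 = 1.08 mm. Power is 71.7% at 45 per arm (noncentrality 2.561) and 67.6% at 41 per arm (2.445). Allowing for the mixture of means raises the drug-arm SD to √(4 + 0.1 × 0.9 × 1.2²) = 2.03 mm and lowers these to 71.0% and 66.9%.
- Half benefit: difference 1.2 × 0.95 = 1.14 mm, power 76.2% and 72.2% (SD 2).
- Complete case, 40.5 against 45, full 1.2 mm effect and no selection assumed: 1.2 / 0.433 = 2.770, power 78.2%.

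**The case against.** The best case for the plan is that its default reading already answers the question. Section 9.1 evaluates every randomised patient; collection is tied to the exchange operation and not to being on drug; thickness is to be analysed by length of drug treatment; and patients off treatment are followed for two years. The authors use the two terms loosely: the synopsis uses both in one paragraph. On this view nothing is wrong except that no sentence repeats the rule for removed patients. A complete-case analysis is in any case declared through the no-imputation rule and the 10% attrition allowance, and counts of non-missing values by cohort are already planned.

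Much of this stands. These points favour continued collection, but they are inferences, whereas Section 5.1 is an explicit instruction and Sections 6.6.1 and 8.5 make a lost specimen a realistic outcome. Length of drug treatment also varies with the time expansion takes, so that analysis does not show that early stoppers are included. An allowance for attrition does not cover outcomes lost through the protocol's own removal rules.

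Three stronger inferences are not supported:
- That removed patients certainly have no specimen. The documents do not settle this, and the consent form, which might, was not available.
- That the result will favour zafirlukast. That needs removed patients to have thicker capsules; if theirs are thinner, the shift reverses.
- That every removal rule is specific to the drug arm. Only 5.1 is so by construction. Sections 6.9 and 6.4 apply to either arm, and 6.9 also covers screening, before randomisation.

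**Conclusion.** The concern holds as an unresolved conflict between the declared analysis population and the removal rules. Followed literally, Section 5.1 loses primary outcomes in one arm of an open-label trial after randomisation, and the documents do not say otherwise. It should be fixed, but it is not a fatal flaw.

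The likely statistical effect is small. Under 10% loss confined to the drug arm, type I error is about 5.8% for a gap as large as the whole planned effect and about 7.3% for a 1.95 mm gap, for which the documents give no support. At 5% loss it stays between 5.2% and 5.6%. With equal losses or no association it is about 5%. The removal rates and gaps are assumptions, and the direction is unknown. The case for acting rests on the conflicting text and on the fact that an uncollected specimen cannot be replaced, not on a large expected bias.

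**What to change.** 1. Reconcile the synopsis (duration of follow-up) and Sections 5.1, 6.2, 6.4, 6.6.1, 6.9 and 8.5 with Table 6 note 5, so that ending study treatment is distinct from leaving the study. Leave every clinical stopping rule unchanged.
2. State that the medial, lateral and anterior capsule specimens are collected at exchange from every randomised patient who reaches it, unless she withdraws consent, and are analysed in the randomised arm.
3. Report missing primary endpoints by arm with reasons. Counts of non-missing values are already planned, so only the reasons are new. A simple missing-data sensitivity analysis is optional.
4. State the power expected when early stoppers are included.

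**Cost.** Wording changes and one table. Collection is feasible because a portion of capsule is normally excised, but the documents do not show that routine excision always yields all three sites, so some patients may have incomplete specimens.

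The statistical price is dilution. If 10% of the drug arm stops early with no benefit, power is about 72% with 45 per arm measured and about 68% with 41. The complete-case figure of about 78% looks better only because it describes a selected group and assumes no selection effect. The declared intention-to-treat analysis already implies this dilution; the plan needs to say so.

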3 STUDY DESIGN

3.1 Characteristics

We propose a 2-arm, 90 patient (45 per cohort) trial in patients who will be undergoing mastectomy with immediate tissue-expander reconstruction to determine whether treatment with zafirlukast (20mg PO BID) can reduce or prevent the development of capsular contracture. All patients undergoing mastectomy with immediate tissue-expander placement will be approached

in clinic at the time of their initial consultation with the plastic surgeon and enrolled in the trial at this point. Approximately 60 women undergo mastectomy with tissue-expander reconstruction at our institution per year, thus enrollment will occur over a two-year period.

Patients will be block randomized 1:1 into two cohorts: treatment with zafirlukast and the standard of care, or standard of care alone. Patients will begin treatment with zafirlukast on post-operative day one (+/- 5 days) following placement of tissue expander(s) after the participant is determined safe from a surgical recovery standpoint. They will be continued on the standard dosing (20mg PO twice per day) of zafirlukast through expander fill. Last dose of Zafirlukast will be administered the day prior to expander implant exchange procedure. Patients will be seen every 1 to 2 weeks for expander fill, and will be assessed clinically (refer to section 6.2 for research visits). The treating physician will determine the frequency of visits based on each patient's expander need.

During expander-implant exchange, three representative sections of the expander capsule will be collected: medial, lateral and anterior capsule specimens. These specimens will be bisected; half will be sent to pathology and half will be collected by the [name] lab. Gross and microscopic determination of capsule thickness will be performed by the pathology department. The [name] lab will fix and stain the tissues to look for the presence of collagen, level of fibrosis, and number of myofibroblasts. Fibrosis level and collagen presence will be determined by performing immunohistochemistry with a Trichrome stain of the tissues, as well as Western blot analysis with Collagen-1. Myofibroblasts will be detected using immunohistochemistry with commercially available antibodies.

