3.3.1 Inclusion Criteria

1. Patients who are scheduled to undergo therapeutic or prophylactic mastectomy with immediate placement of tissue expanders and have a strong family history or hereditary cancer
2. Age \geq 18 years
3. Zafirlukast is pregnancy category B. There are no adequate and well-controlled trials in pregnant women. Therefore, the effects of zafirlukast on the developing human fetus are unknown. For this reason, women of child-bearing potential must agree to use adequate contraception: 2 methods of birth control, prior to study entry and for the duration of study participation. Should a woman become pregnant or suspect she is pregnant while she is participating in this study, she should inform her treating physician immediately.
4. Ability to understand a written informed consent document, and the willingness to sign it
5. At least 4 weeks post-completion of chemotherapy
6. Adequate organ function within 14 days start of study start:
 - a. Absolute neutrophil count (ANC) \geq 1.5 X 10⁹/L
 - b. Hemoglobin (Hgb) \geq 9g/dL
 - c. Platelets (plt) \geq 100 x 10⁹/L
 - d. Potassium within normal range, or correctable with supplements;

- e. AST and ALT $\leq 2.5 \times$ Upper Limit Normal (ULN) or $\leq 5.0 \times$ ULN if liver tumor is present
- f. Serum total bilirubin $\leq 1.5 \times$ ULN
- g. Serum creatinine $\leq 1.5 \times$ ULN, or 24-hr clearance $\geq 60\text{ml/min}$

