6.3 Randomization Procedures

This study is an open-label randomized trial; therefore the investigator and subject will know the treatment administered. Patients will be randomized by a study personnel other than the surgeon. The surgeon and patient will be notified of the patient's cohort immediately post-surgery. Two arms will be tested, with each independent assessment. Patients will be block randomized to either treatment with zafirlukast or the standard of care. Enrollment will continue until 90 patients (45 per cohort) have been enrolled.

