7.0 CORRELATIVE STUDIES

Collection of tissue specimen

At the time expander-implant exchange, a portion of the capsule is normally excised as part of the standard of care. For research purposes, we will collect and study several small pieces of capsular tissue excised at the time of surgery. The tissue collected will be used to determine if zafirlukast can reduce the thickness and scarring of the capsule tissue compared to standard of care.

Handling of specimen

Tissue samples will be fixed in 10% neutral-buffered formalin and embedded in paraffin for further analysis.

Shipping of specimen

Specimen will be processed by the surgical pathology department laboratory affiliated with UCSF.

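### The primary endpoint has no rule for patients with two expanders, and the surgeon knows the cohort when specimens are taken, so the choice of side is open to allocation-aware selection

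*Combined protocol and SAP*

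**What the plan says.** Section 9.1 (Primary analysis) fixes the endpoint at one value per patient: "Capsule thickness will be determined by averaging thickness from three separate specimens per patient". Section 3.1 describes the sampling in the singular: "three representative sections of the expander capsule will be collected: medial, lateral and anterior capsule specimens". Thickness is then measured by the pathology department; whether the readers are blinded is not stated.

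The protocol allows for more than one expander. Section 3.1 starts study drug "following placement of tissue expander(s) after the participant is determined safe from a surgical recovery standpoint", and Section 6.2 repeats the phrase. Inclusion criterion 1 (Section 3.3.1) covers "therapeutic or prophylactic mastectomy with immediate placement of tissue expanders" in patients with a strong family history or hereditary cancer. No criterion restricts entry to unilateral surgery.

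On knowledge of allocation, Section 6.3 says: "This study is an open-label randomized trial; therefore the investigator and subject will know the treatment administered". Section 6.2 adds: "The surgeon and patient will be informed of the assigned cohort immediately post-surgery". The operation meant there is the mastectomy with expander placement, so the cohort is known throughout expansion and at the exchange.

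No section mentions bilateral patients, an index breast, who selects the side, or how readings from two capsules become one value.

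**The concern.** For a kind of patient that the protocol foresees, the primary endpoint is not fully defined. Three sections from one side, three from each side, or three spread over both sides would all fit parts of the text, and they can give different values for the same woman.

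The timing makes this more than a missing detail. The gap would be filled in the operating room by someone who knows the cohort, and no later analysis can undo a side chosen there. If the choice leaned towards the thinner-looking capsule in one arm, the primary comparison would be biased.

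The two sides need not be alike. Section 1.1 says that radiation raises the risk of contracture. Section 3.3.2 excludes only prior chest wall radiation, so one side could be irradiated during the study. Section 9.1 plans radiotherapy as an ANOVA factor and a subgroup variable. Without a side rule, a bilateral patient irradiated on one side has no clear radiotherapy status to go with her single thickness value.

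Precision is a lesser matter. If only one capsule were sampled, the second would contribute nothing, in a trial whose planned power is close to 80%.

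**Working it through.** **Inputs from Section 9.0:** means 2.4 and 1.2 mm (difference 1.2), SD 2 mm in both arms, two-sided alpha 0.05, t-test. The section gives two evaluable sizes, 41 and 45 per arm, so both are used.

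**Assumed, because the documents are silent:** bilateral share b = 0.3 to 0.6; between-breast correlation r = 0.5.

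**1. The plan's own figure.** Effect size 1.2/2 = 0.6.
- 45 per arm: noncentrality 0.6 × √(45/2) = 2.85, 88 df, power 80.4%. The stated figure of more than 80% reproduces.
- 41 per arm: noncentrality 0.6 × √(41/2) = 2.72, 80 df, power 76.5%. The stated beta of 0.18 does not reproduce. That is a separate issue; here 76.5% serves only as a baseline.

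**2. Bias bound, normal model.** If the thinner of two breasts is always taken, a bilateral patient's expected value falls by SD × √((1 − r)/π) = 2 × √(0.5/π) = 0.80 mm. If this happens in one arm only, that arm's mean shifts by b × 0.80:
- b = 0.3: 0.24 mm
- b = 0.6: 0.48 mm

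**3. Bias bound, positive distribution.** Thickness cannot be negative, yet a normal with mean 1.2 and SD 2 puts Φ(−1.2/2) = 27% of values below zero. For a lognormal with mean m, SD 2 and correlation 0.5 on the mm scale:
- s² = ln(1 + 4/m²)
- log-scale correlation ρ = ln(1 + 0.5 × 4/m²)/s²
- shift = m × [1 − 2Φ(−s√((1 − ρ)/2))]

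| Model | s | ρ | Shift per bilateral patient | Arm mean, b = 0.3 | Arm mean, b = 0.6 |
|---|---|---|---|---|---|
| Lognormal, mean 1.2 | 1.15 | 0.66 | 0.44 mm | 0.13 mm | 0.26 mm |
| Lognormal, mean 2.4 | 0.73 | 0.57 | 0.64 mm | 0.19 mm | 0.38 mm |
| Normal | – | – | 0.80 mm | 0.24 mm | 0.48 mm |

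The bound therefore runs from 0.13 to 0.48 mm, or 0.13/1.2 = 11% to 0.48/1.2 = 40% of the target difference.

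**4. Sensitivity.** Under the normal model with b from 0.2 to 0.6 and r from 0.3 to 0.9, the one-arm bound runs from 0.07 to 0.57 mm. Holding the SD at 2 mm, the false-positive rate at 41 per arm would be about 5.3% to 24.5%. At b = 0.4 and r = 0.5 the shift is 0.32 mm and the rate 11.0%. Under the lognormal the shifts are smaller.

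**5. Precision from averaging both breasts.** The variance of the patient value is 4 × [1 − b(1 − r)/2].

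| b | Variance | SD (mm) | Power, 41 per arm | Power, 45 per arm |
|---|---|---|---|---|
| 0 | 4.0 | 2.00 | 76.5% | 80.4% |
| 0.3 | 3.7 | 1.92 | 79.7% | 83.3% |
| 0.6 | 3.4 | 1.84 | 82.9% | 86.3% |

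Over the wider ranges of b and r in step 4, power is 77.0% to 85.5% at 41 per arm and 80.8% to 88.6% at 45.

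**The case against.** A reader might infer that the plan lets the surgeon pick which breast counts and discards the other. The documents do not say so. Section 3.1 describes the sampling generically and is silent on side. The text is also compatible with a fixed side, with sections from each capsule, or with sections spread over both. Choice by the surgeon and loss of the second capsule are possible results of the silence, not stated procedure.

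The size is also open to challenge, and the challenge largely stands. The bilateral share and the correlation are assumptions. The bound needs someone who identifies the thinner capsule every time, in one arm only, although thickness is measured in pathology after collection. The normal model overstates the shift for a positive quantity. The documents give no basis for a realistic central value, so none is offered.

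Radiotherapy is partly dealt with, through the exclusion of prior chest wall radiation and the exploratory ANOVA. What remains is one-sided radiotherapy during the study in a bilateral patient; how often that occurs is unknown.

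Finally, a side rule does not close every route to bias. The unblinded surgeon still decides where to cut within the medial, lateral and anterior areas, and blinding of the pathology reading is not stated. That is true, but it does not weaken the case for closing the one route that a single form field removes.

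**Conclusion.** The concern holds as a gap in the definition of the primary endpoint. The plan sets three specimens per patient from one capsule, foresees patients with two expanders, gives no rule for them, and tells the surgeon the cohort before the exchange. The choice of side is therefore open to allocation-aware selection. Nothing in the documents shows that such selection would occur.

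The 0.13-0.48 mm range is an upper bound under its stated assumptions (30-60% bilateral, correlation 0.5, thinner side always taken in one arm only), and the spread reflects the distribution, the mean and the share. A smaller share or a higher correlation lowers it. Opposite selection in both arms would double the normal-model figure but is more extreme still. The power gain from averaging is modest and rests on the same two unknowns.

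It would be wrong to conclude that one breast per patient makes the t-test invalid. It leaves one independent value per patient. The cost is some precision and, without a side rule, room for selection.

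**What to change.** Amend Sections 3.1, 6.3 and 9.1 to adopt one of two rules.

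- **Index breast.** Record the index side on the randomisation form before the cohort is revealed, and take the three specimens from that side. Section 6.2 already has someone other than the surgeon randomise on the day of surgery, with the cohort disclosed afterwards, so this costs one form field.
- **Both breasts.** Where capsule is excised from both sides anyway, take the three specimens from each and use the mean of all readings, with the patient as the unit of analysis. Section 7.0 notes that "a portion of the capsule is normally excised as part of the standard of care", so the added cost is pathology reading in bilateral patients.

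Under either rule, state in Section 9.1 what value is used if an intended side yields no specimen, and record radiotherapy by side so that the exploratory ANOVA can be matched to the capsule measured.
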